## Protocol Amendment 03 Version number: 1 (electronic 3.0) Date: 01 October 2018

Changes made to the protocol are outlined as follows.

- **To change study acronym.**  
In section: Cover Page, Clinical trial summary  
Rationale: change in study acronym.
- **To replace product code with the International Nonproprietary Name venglustat.**  
In section: throughout the document.  
Rationale: introduction of the International Nonproprietary Name.
- **To describe objective of mGFR substudy - to explore the effect of GZ/SAR402671 on measured GFR.**  
In section: Clinical trial summary - Stage 2; Exploratory objectives; 5.2.3 Exploratory objectives.  
Rationale: description of objective of mGFR substudy.
- **To describe endpoint that will be assessed in mGFR substudy: annualized rate of change in mGFR from baseline to 24 months.**  
In section: Clinical Trial Summary - Stage 2; Endpoints; 9.3 Exploratory endpoints; 9.3.2.  
Rationale: description of endpoint that will be assessed in mGFR substudy.
- **To add description of mGFR substudy.**  
In section: Clinical Trial Summary - Stage 2; Assessment schedule; 1.3, footnote v; 10.1.2.1; 10.1.2.2; 10.3.4; Appendix L.  
Rationale: to include details of mGFR substudy.
- **To clarify that collection of 24-hour urine sample at Visits 5 and 7 will take place only at selected sites which participate in isolation of urinary exosomes.**  
In section: 1.3 footnote l; 9.4.17, Appendix K.  
Rationale: clarification of collection of 24-hour urine sample at Visits 5 and 7.
- **To correct spelling of parameter assessed with the urine dipstick.**  
In section: 1.3 footnote i; 1.4 footnote h; 10.1.1.1; 10.1.2.2; 10.1.2.3.  
Rationale: nitrate corrected to nitrite.
- **To clarify timing of evaluation of V2 ECG reading related to run-in medication at V2 and IMP at V3 administration.**  
In section: 1.3; 1.4 footnote m; 10.1.1.2.  
Rationale: clarification added that Investigator should evaluate V2 ECG reading prior to run-in medication administration; V2 ECG central reader's assessment should be evaluated prior to IMP administration at for Visit 3 only.

- **To add information about tolvaptan’s approval in US.**  
In section: 4.1.2.  
Rationale: update of the status of tolvaptan’s approval.
- **To add clarification that WOCBP should use a highly effective method of contraception during the study.**  
In section: 4.3, 7.1 Inclusion Criteria I09.  
Rationale: clarification of requirement for WOCBP to use a highly effective method of contraception during the study.
- **To clarify the time point of the follow up visit after the final dose of investigational medicinal product.**  
In section: 6.2.1.  
Rationale: clarified that the follow-up visit should occur 30 days after the final dose of investigational medicinal product.
- **To clarify that for patients agreeing to participate in the mGFR substudy of Stage 2, additional entry criteria are listed in Appendix L.**  
In section: 7.  
Rationale: description of additional entry criteria for patients who agree to take part in mGFR substudy of Stage 2.
- **To emphasize that a complete physical examination includes full neurological examination.**  
In section: 9.4.6.  
Rationale: emphasis on the neurological component of the complete physical examination.
- **To establish the plan for handling patients who indicate that they have suicidal thoughts.**  
In section: 9.4.9.  
Rationale: establishing plan for handling patients who indicate that they have suicidal thoughts.
- **To clarify the use of Snellen chart in countries where the Latin alphabet is not used.**  
In section: 9.4.10.  
Rationale: use of Tumbling E distance chart was allowed in countries where Latin alphabet is not used.
- **To remove the phrase that highly effective contraceptive method of birth control may be defined according to the local medical practice and regulations.**  
In section: Appendix A.  
Rationale: “Highly effective contraception” has a specific meaning as defined the Clinical Trial Facilitation Group guidance document on contraception in clinical trials.

## Protocol Amendment 02 Version number: 1 (electronic 2.0) Date: 25 May 2018

Changes made to the protocol are outlined as follows.

- **To supplement description of the exploratory objectives of the study.**

In section: clinical trial summary, 5.1.3, 5.2.3

Rationale: added description of objective to explore the effect of GZ/SAR402671 on type, frequency and dosage of analgesic/over the counter pain medication administration.

- **To detail settings of the placebo run-in period.**

In section: clinical trial summary, 6.1, 6.2.1.

Rationale: single-blind setting added to the description of placebo run-in period in Stage 1 and Stage 2.

- **To add details of stratification of patients by geographic region.**

In section: clinical trial summary, 6.1.

Rationale: stratification of patients by region was added to achieve balance between the treatment arms across the different regions.

- **To clarify inclusion criteria.**

In section: clinical trial summary, 7.1.

Rationale:

- Clarification has been made on inclusion criterion I01 related to the timing of evaluation of this criterion;
- Clarification has been made on inclusion criterion I07 describing situation when patient refuses to initiate treatment with tolvaptan as part of scenario when tolvaptan may not be considered by treating physician as indicated for treatment of patient.

- **To clarify exclusion criteria.**

In section: clinical trial summary, 7.2.1

Rationale:

- Criterion E02 was reworded to emphasize that all Polycystic Kidney Disease-modifying agents should not be administered within 3 months prior to the screening visit;
- Criterion E05 was supplemented with information when patients with positive hepatitis B core antibody, negative HBsAg and negative hepatitis B surface antibody can be enrolled in the study (to exclude occult HBV infection in isolated anti-HBc positive patients).

- **To apply removal of mGFR substudy to the protocol.**

In section: clinical trial summary, 1.4, 3, 5.2.3, 9.3.2, 10.1.2.1, 10.1.2.2, 10.3.4, Appendix A.

Rationale: references to mGFR substudy (including collection of blood samples and Appendix A) were removed from the protocol.

- **To clarify adjustment on stratification factors in the analysis.**

In section: clinical trial summary, 11.4.2.1.1, 11.4.2.2.3, 11.4.5

Rationale: to clarify that adjustment on stratification factors in the analysis for Mayo imaging classification (Mayo Class 1C, 1D and 1E).

- **To improve the precision and accuracy of the BP measurement.**

In section: 1.3, 1.4, 9.4.5.

Rationale: 5-minute rest period was changed to 10-minute rest period; additionally scenario of short-term blood pressure variability between successive measurements was addressed.

- **To clarify screening laboratory assessments.**

In section: 1.3, 1.4

Rationale: to clarify that some assessments done at the beginning of screening may have to be repeated prior to randomization.

- **To detail course of actions when any parameter on the locally performed urinary dipstick is abnormal.**

In section: 1.3, 1.4

Rationale: to specify that in case if any parameter on the urinary dipstick is abnormal, a urine sample should be sent to the central laboratory for quantitative measurement

- **To expand the justification of placebo selected as the control arm.**

In section: 6.5.2

Rationale: Details have been added to justify why tolvaptan is not being used as control arm such as the description of potential discontinuation or failure to initiate the therapy with tolvaptan due to poor tolerability and safety, and possibility of substantial unblinding due to aquaretic effect of tolvaptan.

- **To clarify that enrollment is based on 3 categories of screening eGFR values.**

In section: 7

Rationale: to have adequate representation of patients across eGFR spectrum a minimum of 20% of patients within 3 categories of screening eGFR will be enrolled.

- **To clarify blinding measures related to PK measurements.**

In section: 8.3.1

Rationale: to clarify that only samples collected from patients on active drug will be analyzed and describe measures to ensure blinding at the assay institutions charged for PK measurements.

- **To clarify forbidden concomitant medications.**

In section: 8.8.1

Rationale: to clarify that Polycystic Kidney Disease-modifying agents (eg, somatostatin analogues) are forbidden concomitant medications.

- **To provide details on the method of calculation of eGFR in Asian population of patients and separately in Japanese patients.**

In section: 9.4.2

Rationale: to clarify that for calculation of eGFR in Asian population of patients (except Japanese patients) the Asian-modified CKD-EPI equation will be used; the CKD-EPI Study equation multiplied by a Japanese coefficient of 0.813 will be used for eGFR calculation in Japanese patients.

- **To update and clarify instructions for collection of urine spot.**

In section: 1.3, 1.4, 9.4.3

Rationale: to clarify instructions for collection of urine spot including collection of third spot sample.

- **To provide details on the frequency and scope of ophthalmic examination, to update the system for grading the type and severity of cataract, to remove requirement for lens photography during each lens assessment and requirement for central reading.**

In section: clinical trial summary, 1.3, 1.4, 9.4.10, 10.1.1.2, 10.1.2.2, 10.1.2.3

Rationale: to update the frequency and the scope of ophthalmic exam, to replace LOCSII with LOCSIII, to remove requirement for mandatory lens photography and central reading of lens images.

- **To rename section.**

In section: 9.4.11

Rationale: to change the name of section to Patient reported outcomes.

- **To update description of Patient Global Impression of Change questionnaire.**

In section: 9.4.11.4.

Rationale: to specify timing of the start of assessment and categories of scales.

- **To update items of the Daily symptoms of autosomal dominant polycystic kidney disease diary.**

In section: 9.4.11.6.

Rationale: to regroup pain and nocturia items of the diary and to add an additional item that will direct to the medication entry log.

- **To update information about PK samples collection.**

In section: clinical trial summary, 1.3, 1.4, 9.4.14.1, 10.1.2.1, 10.1.2.2

Rationale: to remove all pre-dose samples on Day1 in Stage 1; to add a post-dose sample on Day1 in stage 2; to move the PK sampling from Month 6 to month 1 in Stage 2; to specify that the post-dose sample of 3 hours can be collected at 3 + or - 1 hour.

- **To detail stopping rules for individual treatment discontinuation in case of ophthalmic examination findings and reduction in eGFR.**

In section: 10.3.3

Rationale: To include a stopping rule for individual treatment discontinuation in case of best corrected visual acuity loss due to posterior subcapsular cataract; to modify period between 2 assessments with confirmed reduction in eGFR that should lead to study treatment discontinuation.

- **To clarify visits and assessments that should be performed if patient prematurely and permanently discontinue study medication.**

In section: clinical trial summary, 10.3.4.

Rationale: to specify visits and assessments that should be performed if patient prematurely and permanently discontinue study medication (end-of-treatment and follow-up visits, PRO assessments, efficacy and safety assessments at visits Month 18 and Month 24).

- **To describe secondary analysis that will explore a potential acute hemodynamic effect.**

In section: 11.4.2.1.1

Rationale: to describe secondary analysis that will explore a potential acute hemodynamic effect using TKV data assessed from 1 month to 18 months.

- **To correct information of the section.**

In Section: 12.2

Rationale: to remove requirement that the written informed consent form can be signed and dated by the patient's legally acceptable representative.

- **To clarify information related to highly effective contraceptive method of birth control.**

In section: Appendix B.

Rationale: to specify that highly effective contraceptive method of birth control may be defined according to the local medical practice and regulations.

- **To clarify that Isolation of Urinary Exosomes analysis is part of ADPKD biomarkers assessment (required tests of the protocol).**

In section: Appendix L.

Rationale: to specify that isolation of Urinary Exosomes analysis is part of ADPKD biomarkers assessment and is covered by informed consent of EFC15392 study.

## Protocol Amendment 01 Version number: 1 (electronic 1.0) Date: 19 April 2018

Changes made to the protocol are outlined as follows.

- **To clarify possible course of action with regard to the study drug dose in ongoing patients in Stage 1 after DMC review of safety data and dose selection for Stage 2.**  
In section: 6.1  
Rationale: described possible course of action with regard to the study drug dose in ongoing patients in Stage 1 that could be recommended by DMC to Sponsor after dose selection for Stage 2.
- **To clarify inclusion criteria.**  
In section: clinical trial summary, 7.1.  
Rationale: clarification has been made on inclusion criteria I01 and I02 to better define the targeted population and criterion I07 to describe written ICF collection before any study procedure.
- **To clarify exclusion criteria.**  
In section: 7.2.1, 7.2.3.  
Rationale: criterion E09 was modified to better detail uncontrolled medical conditions, criterion E10 was modified to address country-specific exclusion criteria, criterion E16 was revised to indicate the limits of total and direct bilirubin that are allowed for inclusion of patients with Gilbert's syndrome.
- **To detail timing of evaluation of the secondary and exploratory endpoints.**  
In section(s): clinical trial summary, 9.2.2, 9.2.3.3, 9.3.3.  
Rationale: Details on the time point of evaluation of secondary and exploratory endpoints were included.
- **To add a stopping rule for individual treatment discontinuation.**  
Section 10.3.3  
Rationale: to include a stopping rule for individual treatment discontinuation in case of accelerated disease progression based on eGFR reduction.
- **To include blood pressure control recommendations.**  
In Section: 10.6.  
Rationale: Safety management was modified to include blood pressure control recommendations if patient requires modification of antihypertensive therapy during study participation.
- **To clarify that mGFR substudy is optional for eligible patients.**  
In section Appendix A, Section 4.  
Rationale: To clarify that mGFR substudy is optional for eligible patients.

## **Appendix O Contingency Measures for a regional or national emergency that is declared by a governmental agency**

A regional or national emergency declared by a governmental agency (eg, public health emergency, natural disaster, pandemic, terrorist attack) may prevent access to the clinical trial site.

Contingency procedures are suggested below and in sections ([Section 7.2.4](#), [Section 8.1.2](#), [Section 9.4](#), [Section 10](#), [Section 10.3.1](#), [Section 12.2](#)) for an emergency that prevents access to the study site, to ensure the safety of the participants, to consider continuity of the clinical study conduct, protect trial integrity, and assist in maintaining compliance with Good Clinical Practice in Conduct of Clinical Trials Guidance. Sponsor agreement MUST be obtained prior to the implementation of these procedures for the duration of the emergency.

During the emergency, if the site will be unable to adequately follow protocol mandated procedures, alternative treatment outside the clinical trial should be proposed, and screening, enrollment, randomization and/or administration of study treatment may be temporarily delayed/halted.

The participant or their legally authorized representative should be verbally informed prior to initiating any changes that are to be implemented for the duration of the emergency (eg, study visit delays/treatment extension, use of local labs).

Attempts should be made to perform all assessments in accordance with the approved protocol to the extent possible. In case this is not possible due to a temporary disruption caused by an emergency, focus should be given to assessments necessary to ensure the safety of participants and those important to preserving the main scientific value of the study.

The following contingencies may be implemented for the duration of the emergency (after Sponsor agreement is obtained) to make clinical supplies available to the participant for the duration of the emergency: the Direct-to-Patient (DTP) supply of venglustat from the site where allowed by local regulations and agreed upon by the participant. Direct-to-Patient supply of IMP is not contingent on availability of contemporaneous laboratory results or other study specific assessments.

Procedures to be considered in the event of a regional or national emergency declared by a governmental agency (where allowed by local regulations) if onsite visits are not possible:

- Phone contacts are to be performed in place of an onsite study visits and per study protocol schedule. Essential data (that can be checked via interview to evaluate patient safety) to be captured via phone contact and documented in the source records include, but is not limited to, AEs, SAEs, change in or new concomitant medications, urine pregnancy test results, IMP compliance, potential signs of depressed mood, complaints about changes in vision, vital signs (if patients can measure temperature and BP at home). Visit ePROs (questionnaires) should be completed by the patient in the eDiary as usual. eDiary data can still be checked online by the investigator/site team prior to calling the patient to ensure any follow-up questions or findings can be discussed.

- If it is feasible and there is no additional risk for a patient from the hazard that led to declaration of national emergency, consider performing blood tests in local laboratories:
  - blood chemistry: at the minimum blood creatinine, AST, ALT, eGFR calculated with Chronic Kidney Disease Epidemiology Collaboration equation;
  - complete blood count.
- Patients with a recent eGFR **>45 mL/min/1.73 m^2**, may continue IMP up to 6 months, without having an on-site visit.

Patients with a recent eGFR **≤45 and >30 mL/min/1.73 m^2**, may continue IMP up to 3 months, without having an on-site visit. Patient who are not be able to repeat eGFR in 3 months will have to interrupt the treatment. Temporary IMP discontinuation will need to be registered in IRT.

Patients with a recent eGFR **≤30 and ≥25 mL/min/1.73 m^2**, who are not be able to repeat creatinine in 30 days will have to interrupt the treatment. If eGFR result repeated in 30 days is below 30 mL/min/1.73 m^2, the patient will have to stop the treatment permanently.

- When phone contact is performed in place of an onsite study visits, assessments of efficacy and safety data that cannot be obtained remotely [eg, MRI, ECG, ophthalmological and neurological examination] will be performed when patients are able to resume normal site visits. Safety assessment that cannot be obtained remotely may be performed prior to next regular onsite visit if Investigator considers that this is clinically indicated and feasible, and that this will not involve an additional risk for a patient from the hazard that led to declaration of national emergency.

New screenings during a regional or national emergency declared by a governmental agency can be performed only if allowed by local competent authorities and after Sponsor's agreement is obtained.

If a rescreened patient was screen-failed during a regional or national emergency for reasons not related to eligibility, rescreening shall be permitted when the situation normalizes.

If eligibility assessment cannot be performed due to department/service shutdowns (MRI, ophthalmology, etc) during the screening period, the patient cannot be randomized, and screening period can be extended with randomization after site will be able to reopen. In such scenario, certain screening assessment will have to be repeated before Visit 3:

- Blood chemistry (if >2 weeks after Visit 2)
- CBC (if >4 weeks after Visit 1)
- BCVA and lens cataract grading according to WHO simplified cataract grading system (if >3 months from Visit 2 eye exam)
- ECG (if >3 months from Visit 2 ECG test)
- BDII (if >2 weeks after Visit 2)
- MRI (decision on case by case basis: if >1-3 month before Visit 3)

If eligibility was confirmed but patient cannot attend site to perform Visit 3 because of a regional or national emergency declared by a governmental agency, a remote Visit 3 (randomization) can be performed where allowed by local regulations under condition that the Direct-to-Patient (DTP) supply of venglustat from the site is allowed by local regulations and agreed upon by the participant, and a home health vendor service is in place to visit patient in 1 month (for Visit 4) to collect laboratory samples and assess adverse event after 1 month on the double-blind treatment.

For a remote Visit 3, a home health vendor should visit the patient at least one day before the remote Visit 3 to collect blood pressure measurements, assess run-in medication compliance, adverse events, concomitant medications and perform urine pregnancy test (for WOCBP).

On the day of the remote Visit 3, the Investigator will evaluate assessments performed and provided by home health vendor, ePROs completed by the patient in the eDiary, and will randomize patient if eligibility is reconfirmed. If patient is randomized, IMP will be sent to patient via DTP process. Site will need to follow up via phone with the patient once IMP is delivered.

Contingencies implemented due to emergency will be documented.

Signature Page for VV-CLIN-0272048 v7.0  
efc15392-16-1-1-amended-protocol07

Approve & eSign	[Redacted]
	[Redacted]

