--	--

ASSESSMENT SCHEDULE	
Stage 1
 
Efficacy assessments: MRI during screening period (at Visit 1 or Visit 2), Months 1, 9, and 18. eGFR (CKD-EPI) at screening, run-in, baseline, Month 1, Month 3, and then every 3 months.
 
Safety/tolerability assessments: Vital signs, physical examination, clinical laboratory evaluation will be performed at all visits. Ophthalmological assessments will be performed at Months -0.5, 6, 12, 18, and 24. Beck Depression Inventory-II will be assessed at Months -0.5, 3, and then every 3 months.
 
Biomarker assessments: Screening, Months 1, 6, 12, 18, 24, and at 30 days follow-up (Month 25).
 
PK assessments: Blood samples for plasma venglustat concentrations assessment will be collected in all patients at following visits:
 

• Day 1: 3 (±1) hour post dose.

• Month 1: pre-dose and 3 (±1) hours post dose.

• 6 months and 18 months: pre-dose sample.

 
Patient Reported Outcome (PRO) Assessments:
 
Pain (BPI) and fatigue (BFI) data will be collected at the baseline visit and at each study visit prior to administration of procedures and the disease and treatment discussion with the patients. Patient global impression of severity will be collected at run-in, baseline and Months 3, 12, 18, and 24. Patient global impression of change will be collected at Months 3, 12, 18, and 24. Health status (EQ-5D-5L) will be collected at baseline and Months 3, 6, 12, 18, and 24.
 
Daily diary data on symptoms of ADPKD (pain: BPI Item 3, fatigue: BFI Item 3, and nocturia) will be entered by the patients for specified consecutive days during the administration period prior to Baseline visit, from Baseline visit to Month 3, and prior to the site visit at Months 12, 18, and 24.
 
Patients who prematurely and permanently discontinue study medication should complete rapidly (within 7 days) an end of treatment assessment visit. End-of-treatment visit should include all procedures of Visit 12 and additionally a PK sample should be collected. In 30 days, a Follow-up visit should be performed. Investigator should ask patient to continue study visits for safety and efficacy assessments up to and including the last scheduled visit, if possible. If the patient refuses to attend all scheduled visits and to continue answering all PRO questionnaires, Investigator should ask the patient to continue answering questions of "Daily symptoms of ADPKD" diary, and also return to the site at Month 18 to have at least MRI performed, and at Month 24 to have at least blood sample (for eGFR) collected. Other assessments planned at Month 18 and/or Month 24 should also be done if possible.
 
Stage 2
 
Efficacy assessments: MRI during screening period (at Visit 1 or Visit 2) and Month 18. eGFR (CKD-EPI) at screening, run-in, baseline, Month 1, Month 3, and then every 3 months.
 
Iohexol will be administered in a substudy in approximately 15% of patients at the baseline visit, Months 12 and 24 to evaluate mGFR.
 
Safety/tolerability assessments: Vital signs, physical examination, clinical laboratory evaluation will be performed at all visits. Ophthalmological assessments will be performed at Months -0.5, 6, 12, 18, and 24. BDI-II will be assessed at Months -0.5, 3, and then every 3 months.
 
Biomarkers: Screening, Months 6, 12, 18, 24, and at 30 days follow-up (Month 25).

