#### **11.4.2.1.2 Stage 2**

In Stage 2, the primary efficacy endpoint is the annualized rate of change in eGFR (CKD-EPI equation).

The analysis of eGFR will be similar to those of TKV, with the exception that no log transformation will be used for eGFR. Baseline eGFR will be defined for each patient as the average of eGFR values assessed prior to randomization.

Primary analysis in Stage 2 will combine all data from Stage 1 and Stage 2 available from baseline to the end of the 24-month double-blind core treatment period. Primary analysis will include all observed eGFR data in randomized patients, regardless of whether or not patients completed the treatment period (treatment policy strategy). Patients who prematurely and permanently discontinue study medication will be requested to obtain eGFR at 24 months. All efforts will be made to minimize the amount of missing data.

Missing data will be handled using methods similar to those of TKV. Additional details are included in [Appendix J](#).

A secondary analysis will estimate the effect of venglustat while patients are still on treatment.

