4 STATISTICAL ANALYSES

4.1 GENERAL CONSIDERATIONS

In general, continuous data will be summarized using the number of observations available, mean, standard deviation (SD), median, [Q1, Q3] minimum, and maximum. Categorical and ordinal data will be summarized using the count and percentage of participants.

The baseline value is defined as the last available value before or equal to the first dose of double-blind investigational medicinal product (IMP). For participants randomized but not exposed, the baseline value is defined as the last available value before or equal to the date and time of randomization.

Baseline eGFR is defined for each participant as the average of eGFR values assessed prior or equal to first IMP, or randomization for participants randomized and not exposed.

Baseline of patient daily diaries scores is defined for each participant as the average of the assessments during the 7 days prior the 1st IMP or prior randomization for participants randomized and not exposed.

Baseline of urine osmolality is defined as the average of the 3 separate assessments within the 3 days prior or equal to the baseline visit (Visit 3).

Primary efficacy analyses will be conducted on Stage 1 ITT population and on combined Stage 1 and Stage 2 ITT populations (see Section 3), including all data available at the time of database lock from baseline to Month 24:

• Participants from Stage 2 with an eGFR between 30 and 44.9 mL/min/1.73 m² at screening will not be included in the primary efficacy analysis. A supplemental descriptive efficacy analysis on these participants will be performed separately (see Section 3 and Section 4.3.2.4).

Safety analyses will be conducted in the extended combined Stage 1 and Stage 2 population (see Section 3) including all data available from baseline to the end of the 24-month double-blind treatment period. Unless otherwise specified, analyses will be performed by intervention group (and overall for baseline and demographics characteristics).

Observation period

The observation period will be divided into 4 segments:

- The **pre-treatment period** is defined as the period up to first IMP administration.
- The **treatment-emergent** (TE) **period** is defined as the period from the first IMP administration up to the last IMP administration in EFC15392 study +30 days or up to the first visit in LTS15823 study, whichever comes earlier. The treatment-emergent period includes the following 2 periods:

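### Appendix O's task list for the home visit before a remote Visit 3 omits the scheduled Visit 3 blood sample and the spot and 24-hour urine, so as listed these patients have no urine osmolality baseline and one eGFR reading fewer at baseline

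*Protocol*

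**What the plan says.** **Remote pathway (Protocol Appendix O).** If eligibility is confirmed but the patient cannot reach the site, Visit 3 may be done remotely. Beforehand, "a home health vendor should visit the patient at least one day before the remote Visit 3", and the vendor's tasks are to "collect blood pressure measurements, assess run-in medication compliance, adverse events, concomitant medications and perform urine pregnancy test (for WOCBP". The first dose comes later: "If patient is randomized, IMP will be sent to patient via DTP process". The pathway is open only if "a home health vendor service is in place to visit patient in 1 month (for Visit 4) to collect laboratory samples". Laboratory sampling is therefore required of the vendor, but only at Visit 4, after a month on treatment.

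**Normal Visit 3 (Protocol 1.3, 1.4 and 10.1.2.1).** Chemistry, hematology, spot urine and 24-hour urine are all scheduled, and laboratory assessments must precede double-blind dosing.

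**eGFR baseline.** The Clinical trial summary schedules "eGFR (CKD-EPI) at screening, run-in, baseline, Month 1, Month 3, and then every 3 months", which gives three pre-dose readings. Protocol 11.4.2.1.2: "Baseline eGFR will be defined for each patient as the average of eGFR values assessed prior to randomization". SAP 4.1: "Baseline eGFR is defined for each participant as the average of eGFR values assessed prior or equal to first IMP".

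**Osmolality baseline.** Protocol 9.4.3 starts osmolality at Month 0; the flow charts show no urinary-marker sample at Visits 1 or 2. SAP 4.1: "Baseline of urine osmolality is defined as the average of the 3 separate assessments within the 3 days prior or equal to the baseline visit".

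**The concern.** The list for the remote Visit 3 is the specific instruction a vendor will work from, and it names no laboratory blood sample and no urine for osmolality. The two omissions differ in weight.

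- **Osmolality.** Visit 3 is the only pre-dose collection. If it is missed, change from baseline cannot be computed for that patient. Appendix O defers assessments that cannot be done remotely until site visits resume, but a pre-dose sample cannot be taken after dosing has begun.
- **eGFR.** Two readings remain. Both can serve to confirm eligibility (criterion I 03), and the missing one is the only scheduled pre-dose reading without that role. Baseline is noisier for the slope and for the confirmed 30% and 40% decline endpoints, but it exists.

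The gap looks avoidable. The vendor is in the home before the first dose, its service must already cover laboratory samples at Visit 4, and Protocol 10.1.1.2 issues the urine containers at Visit 2.

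**Working it through.** **1. Check of the model against the plan's own figures.** I re-simulated the design with the parameters of Protocol 11.1 and Appendix J: 80 per arm in Stage 1 plus 160 per arm in Stage 2, 10% dropout at 2 years, futility at one-sided p > 0.30, and levels 0.04, 0.001, 0.049 and 0.01. Slopes were estimated by generalised least squares with known variances.

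| | Stated | Re-simulated |
|---|---|---|
| Scenario 2, eGFR | 87.0% | 86.4% |
| Scenario 2, TKV | 89.0% | 88.2% |
| Scenario 2, futility | 3.1% | 3.2% |
| Scenario 1, eGFR | 90.1% | 89.8% |
| Scenario 1, TKV | 92.6% | 92.4% |

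The runs used 4000 trials for Scenario 2 and 2500 for Scenario 1. The agreement is close enough to use the same variance components below.

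**2. Count of pre-dose readings.**

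| | Planned | Remote Visit 3 as listed |
|---|---|---|
| eGFR | 3 (Visits 1, 2, 3) | 2 (Visits 1, 2) |
| Osmolality | 3 (all tied to Visit 3) | 0 |

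**3. Error in baseline eGFR.** The residual SD is 6.34 (Protocol 11.1), so the SD of a mean of k readings is 6.34/√k.

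- k = 3: 6.34/√3 = 3.66
- k = 2: 6.34/√2 = 4.48, which is √(3/2) = 1.22 times as large

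**4. One patient's eGFR slope.** Appendix J gives random-intercept variance 106.81, slope variance 3.90, covariance 5.36 and residual variance 40.26. With X = [1, t], G the random-effects matrix and V = XGXᵀ + 40.26·I, the slope variance is the (2,2) element of (XᵀV⁻¹X)⁻¹. Pre-dose times are −30, −15 and 0 days; later visits are at Months 1, 3, 6 and so on.

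| Pre-dose eGFR | Slope variance to Month 24 |
|---|---|
| Three readings | 10.53 |
| Two readings (no Visit 3) | 11.26 |
| One reading at time 0 (powering assumption) | 12.83 |

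Without versus with Visit 3, the ratio is 11.26/10.53 = 1.07. With follow-up only to Month 9 it is 1.09. Against the powering assumption, 11.26/12.83 = 0.88, so two readings still give about 12% less variance than the sample size calculation assumed.

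**5. Power of the Stage 2 comparison.** This is an approximation: 240 versus 240 completers (80 + 160 per arm), the time-0 value taken as the mean of k readings, zero intercept-slope covariance, true difference 0.30 × 3.66 = 1.098, two-sided level 0.049. Power is Φ(1.098/SE − 1.969).

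| Assumed remote share | SE of slope difference | Power |
|---|---|---|
| 0% | 0.2994 | 95.5% |
| 5% | 0.2999 | 95.5% |
| 20% | 0.3015 | 95.3% |
| 30% | 0.3026 | 95.2% |

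The loss at 30% is under 0.5 point. These powers exceed the plan's 87.0% because they leave out dropout, the dose contrasts, the futility look and the dependence on the TKV test; only the differences between rows matter. One reading at time 0 for everyone gives 91.7%, and two readings for everyone give 94.2%.

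**6. Patients without an osmolality baseline.** The documents give no count. If 5% to 20% of the 400 Stage 2 patients were randomised remotely, that is 20 to 80. These are upper figures, because SAP 4.5.2 excludes patients on oral diuretics at first dose.

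**7. Urine timing.** Protocol 9.4.3 takes the first spot two days before the visit, ends the 24-hour collection on the visit morning and takes the second spot that day. A vendor calling earlier cannot collect urine due on the morning of Visit 3. If the collection is timed from the vendor visit instead:

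- vendor 1 day before Visit 3: first spot 1 + 2 = 3 days before, inside the SAP window
- vendor 2 or 3 days before: first spot 4 or 5 days before, outside it

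Appendix O sets no upper limit on how early the vendor may call.

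**The case against.** The best defence is that the list is not said to be exhaustive. Its items largely match the eligibility checks repeated at Visit 3, and the investigator then randomises if eligibility is reconfirmed. Appendix O also asks sites to attempt all protocol assessments where possible, and suggests local blood tests including creatinine where feasible. A local pre-dose creatinine is not barred from the eGFR analyses: the central-only rule in SAP 5.4 governs the by-visit windows, the slope analyses take planned and unscheduled assessments, the baseline definition sets no central-only limit, and SAP 4.3.2.4 accepts local or central values for the decline endpoints.

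This stands for eGFR: loss of the third reading is possible, not certain. It does not stand for urine. The attempt clause is general, the local tests are optional and blood only, and nothing replaces the Visit 3 urine. The repeat of blood chemistry more than 2 weeks after Visit 2 belongs to the separate extended-screening case.

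It is also fair that the pathway applies only in an emergency with Sponsor agreement, that osmolality is exploratory and only summarised by visit, and that the SAP defines a population without COVID-19 disruption. These points limit the weight, but none supplies a baseline.

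Three stronger readings are tempting, and the documents support none of them:

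- **No blood or urine is taken at all.** A urine pregnancy test is listed for women of childbearing potential.
- **Baseline eGFR is lost, or the primary endpoint is compromised.** Visits 1 and 2 remain, and they give more information than the powering assumed.
- **There is no baseline urine protein.** Visit 1 urinalysis includes dipstick protein, with central quantification if abnormal.

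**Conclusion.** The omission is real and its consequences are small. Followed as written, the remote Visit 3 list leaves a patient with no SAP-defined osmolality baseline, and that loss cannot be recovered later. It affects an exploratory, descriptive endpoint in patients not on diuretics. For eGFR, unless a local test is done, baseline error SD rises from 3.66 to 4.48 and that patient's slope variance by about 7% at 24 months. The effect on power for the primary slope is negligible.

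The eGFR figures rest on the Appendix J variance components and the nominal visit times. The power figures rest on the approximation in step 5 and an assumed remote share. The number of patients randomised remotely is not given. This is a cheap improvement, not a threat to the primary analysis.

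**What to change.** In Appendix O:

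1. Add to the vendor's pre-dose visit the central-laboratory chemistry and hematology draw and pick-up of the spot and 24-hour urine.
2. Schedule that visit one day before the remote Visit 3, replacing the open-ended lower limit.
3. Time the Protocol 9.4.3 urine collection from the vendor visit for these patients, so that all samples precede the first dose and fall within the 3-day window of SAP 4.1.

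As an alternative to tying the timing to Visit 3, the SAP can define the osmolality baseline relative to the vendor visit for these patients. In either case the SAP should say how patients without a Visit 3 baseline are handled and report how many there are. Since SAP 4.9.2 records the decision to discontinue the study, that statement is the part that still helps for patients already randomised remotely.

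The cost is a short addition to Appendix O, a longer home visit, and sample shipping for these patients only. Simply listing the Visit 3 urine without re-timing its collection would not work, for the reason in step 7.
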